| Objectives | 
Primary objective:
 
 • Evaluate the percentage of repigmentation observed one month after the end of three months of treatment measured on an objective layer by image analysis; 
Secondary objectives: Evaluate:
 
 • the percentage of repigmentation observed after one, two and three months of treatment measured on an objective layer by image analysis; • the ability of the product to maintain the human body in good condition (cutaneous acceptability) by clinical examination by the dermatologist; • Patient satisfaction using a visual analogue scale from 0 to 10. • The illustrative effect using standardized photographs; • The quantity of product by weighing the tubes. • The occurrence of possible adverse effects. | | | | | | | | | | | | | | | | | | | | | | | | | | | | | | | | | | | | | | | | | | | | | | | | | | | | | | | | | | | | | | | | | | | | | | | | | | | | | | | | | | | | |
|---|--|---------|-----------------|---------|---------|-------|----|----|-------------------|---|---|---|---|---|---|---|---|---|---|---|---|---|--|---|---|---|---|---|---|--|---|---|---|---|---|---|---|---|---|---|---|---|---|---|---|---|---|---|---|---|---|---|---|---|---|---|---|---|---|---|---|---|---|---|-------------------------------|---|---|---|---|---|---|--|----------|---------|---------|---------|---------|-------|--|----------|---|---|---|---|-------|
| | 
 • Study in proof of concept; • Double blind study; • Comparative study, versus placebo in intra-individual; • Three parallel groups testing different dosages / combinations of treatments; • Randomized. | | | | | | | | | | | | | | | | | | | | | | | | | | | | | | | | | | | | | | | | | | | | | | | | | | | | | | | | | | | | | | | | | | | | | | | | | | | | | | | | | | | | |
| Methodology | | | | | | | | | | | | | | | | | | | | | | | | | | | | | | | | | | | | | | | | | | | | | | | | | | | | | | | | | | | | | | | | | | | | | | | | | | | | | | | | | | | | | |
| Kinetics | 
  
 	Selection visit	D0	M1	M2	M3	M4	
   
 Weighing products	•	•	
 
 Information of the volunteer about the conditions of the study and collection of his informed consent	•	•	
 
 Verification of inclusion and non-inclusion criteria	•	•	
 
 Realization of a standardized photograph of each target lesion	•	•	
 
 Shifting and identifying the perimeter of each target lesion on a layer sheet	•	•	
 
 Clinical examination by the dermatologist	•	•	
 
 Application of the product by the patient at home	•	•	
 
 Scoring on a visual analogue scale by the patient	•	•	
 
 Collection of adverse effects	•	•	
 
 Distribution (d) / return (r) of daily log	• (d)	• (r/d)	• (r)	
 
 Distribution (d) / return (r) of the studied product	• (d)	•	•	•	•	• (r)	
  
 | | Selection visit | D0 | M1 | M2 | M3 | M4 | Weighing products | • | • | • | • | • | • | Information of the volunteer about the conditions of the study and collection of his informed consent | • | • | • | • | • | • | Verification of inclusion and non-inclusion criteria | • | • | • | • | • | • | Realization of a standardized photograph of each target lesion | • | • | • | • | • | • | Shifting and identifying the perimeter of each target lesion on a layer sheet | • | • | • | • | • | • | Clinical examination by the dermatologist | • | • | • | • | • | • | Application of the product by the patient at home | • | • | • | • | • | • | Scoring on a visual analogue scale by the patient | • | • | • | • | • | • | Collection of adverse effects | • | • | • | • | • | • | Distribution (d) / return (r) of daily log | • (d) | • (r/d) | • (r/d) | • (r/d) | • (r/d) | • (r) | Distribution (d) / return (r) of the studied product | • (d) | • | • | • | • | • (r) |
| | Selection visit | D0 | M1 | M2 | M3 | M4 | | | | | | | | | | | | | | | | | | | | | | | | | | | | | | | | | | | | | | | | | | | | | | | | | | | | | | | | | | | | | | | | | | | | | | | | | | | | | | | |
| Weighing products | • | • | • | • | • | • | | | | | | | | | | | | | | | | | | | | | | | | | | | | | | | | | | | | | | | | | | | | | | | | | | | | | | | | | | | | | | | | | | | | | | | | | | | | | | | |
| Information of the volunteer about the conditions of the study and collection of his informed consent | • | • | • | • | • | • | | | | | | | | | | | | | | | | | | | | | | | | | | | | | | | | | | | | | | | | | | | | | | | | | | | | | | | | | | | | | | | | | | | | | | | | | | | | | | | |
| Verification of inclusion and non-inclusion criteria | • | • | • | • | • | • | | | | | | | | | | | | | | | | | | | | | | | | | | | | | | | | | | | | | | | | | | | | | | | | | | | | | | | | | | | | | | | | | | | | | | | | | | | | | | | |
| Realization of a standardized photograph of each target lesion | • | • | • | • | • | • | | | | | | | | | | | | | | | | | | | | | | | | | | | | | | | | | | | | | | | | | | | | | | | | | | | | | | | | | | | | | | | | | | | | | | | | | | | | | | | |
| Shifting and identifying the perimeter of each target lesion on a layer sheet | • | • | • | • | • | • | | | | | | | | | | | | | | | | | | | | | | | | | | | | | | | | | | | | | | | | | | | | | | | | | | | | | | | | | | | | | | | | | | | | | | | | | | | | | | | |
| Clinical examination by the dermatologist | • | • | • | • | • | • | | | | | | | | | | | | | | | | | | | | | | | | | | | | | | | | | | | | | | | | | | | | | | | | | | | | | | | | | | | | | | | | | | | | | | | | | | | | | | | |
| Application of the product by the patient at home | • | • | • | • | • | • | | | | | | | | | | | | | | | | | | | | | | | | | | | | | | | | | | | | | | | | | | | | | | | | | | | | | | | | | | | | | | | | | | | | | | | | | | | | | | | |
| Scoring on a visual analogue scale by the patient | • | • | • | • | • | • | | | | | | | | | | | | | | | | | | | | | | | | | | | | | | | | | | | | | | | | | | | | | | | | | | | | | | | | | | | | | | | | | | | | | | | | | | | | | | | |
| Collection of adverse effects | • | • | • | • | • | • | | | | | | | | | | | | | | | | | | | | | | | | | | | | | | | | | | | | | | | | | | | | | | | | | | | | | | | | | | | | | | | | | | | | | | | | | | | | | | | |
| Distribution (d) / return (r) of daily log | • (d) | • (r/d) | • (r/d) | • (r/d) | • (r/d) | • (r) | | | | | | | | | | | | | | | | | | | | | | | | | | | | | | | | | | | | | | | | | | | | | | | | | | | | | | | | | | | | | | | | | | | | | | | | | | | | | | | |
| Distribution (d) / return (r) of the studied product | • (d) | • | • | • | • | • (r) | | | | | | | | | | | | | | | | | | | | | | | | | | | | | | | | | | | | | | | | | | | | | | | | | | | | | | | | | | | | | | | | | | | | | | | | | | | | | | | |

| Foreseen dates | Product reception | Study start | Study end | 1 st results by e-mail | | |
|------------------|--|---------------|------------------|-----------------------------------|--|--|
| | October 31, 2018 | October, 2019 | May, 2020 | August, 2020 | | |
| Products | Reference | Form | Application zone | | | |
| | Product ref : 16300.04 Lot 120918A | | | | | |
| | Placebo Ref : 16300.06 Lot 120918B | | | | | |
| Study Population | Specific inclusion criteria | | | | | |
| | 
 • Sex: female and male; • Age: 18 years old and above; • Patients with stable non-segmental vitiligo lesions (defined by no new lesions or lesions existing for at least 3 months, absence of hypochromic margins in Wood's light and absence of confetti depigmentation); • Patients with 2 to 6 symmetrical lesions (1 to 3 on each side). These lesions (macules) will be treated for a minimum surface of 2 cm² and a maximum surface of 100 cm². | | | | | |
| | Number of subjects minimum 12 distributed into groups of 4 | | | | | |

1. STUDY PROCESS

The study is carried out on cosmetic products whose safety has been assured by the Sponsor.

Its aim is to further confirm, under normal and reasonably foreseeable use conditions, the capacity of products to maintain human body in good condition.

- See ethical requirements and regulatory standards in **Appendix 6**.

This study will be conducted under the following conditions:

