1.2.2. Application

| | Zone | Frequency | Mode |
|--|------|--|------|
| Product ref : 16300.04 Lot 120918A | Body | 
 • Group A : 4 patients; Lithium liposome 1 application / day (evening) on target lesions on one side of the body, placebo 1 application / day (evening) on contralateral target lesions and excimer lamp on target lesions on the two sides; | |
| Placebo ref: 16300.06 Lot 120918B | Body | 
 • Group B : 4 patients; Liposomal Lithium 2 applications / day (morning and evening) on target lesions on one side of the body, placebo 2 applications / day (morning and evening) on contralateral target lesions and excimer lamp on target lesions on the two sides; • Groupe C : 4 patients; Lithium liposome 2 applications / day (morning and evening) on one side, placebo 2 applications / day (morning and evening) on contralateral target lesions. | |

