1.3. STUDY STAGES

BEFORE THE BEGINNING OF THE STUDY

Technician:

- weighs the study products before their use.

Twice a week:

Patients of both groups A and B come to the hospital where the lesions will be exposed with a Quantel 308 excimer lamp that delivers a narrow UVB spectrum centered of a wavelength of around 308nm. This lamp makes it possible to perform phototherapy localized on the target lesion. Fluences will be performed twice a week throughout the duration of the study.

ON D0**Patients:**

- come to the investigation center without having applied any product to the body since the previous evening;
- are informed about the trial objectives, the procedures and the risks of the study with the information sheet;
- sign two copies of the Consent Form.

Dermatologist:

- verifies inclusion and non-inclusion criteria;
- performs a standardized photo of each target lesion;
- traces and identifies the perimeter of each target lesion (1 to 3 on each side) on a tracing sheet (the natural marks such the scars, moles, tattoos or others will be also reported on the tracing sheet in order to easily find the target lesions);
- performs a clinical examination of the skin on the application area;
- asks the subjects about their usual unpleasant sensations;
- explains to the subjects the product application conditions and frequency;
- gives to the subjects:
 - the product to be used according to the instructions in 2.1.2 and 2.2.2,
 - the daily log to write down their possible unpleasant sensations or medications,

ON M1 (last application being done the previous day)**Subjects:**

- return to the hospital with no product applied to the body since the previous evening;
- bring back their daily log;

Dermatologist:

- performs a standardized photo of each target lesion;
- traces and identifies the perimeter of each target lesion (1 to 3 on each side) on a tracing sheet (the natural marks such the scars, moles, tattoos or others will be also reported on the tracing sheet in order to easily find the target lesions);
- performs a clinical examination of the skin on the application area;
- asks the subjects about the unpleasant sensations they felt during the study and assesses the cutaneous acceptability of the study product;
- collection of the concomitant treatments and undesirable effects.

On M2 (the last application being done the previous night):**Subjects:**

- return to the hospital with no product applied to the body since the previous evening;

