2.4. CUTANEOUS ACCEPTABILITY

Before (D0) and after product use (M1, M2, M3), the subjects body is examined by the dermatologist to assess each of the following parameters:

[figure not shown]
| | NONE | VERY MILD | MILD | MODERATE | SEVERE |
|----------------|--------------------------|--------------------------|--------------------------|--------------------------|--------------------------|
| Erythema |  |
| Edema |  |
| Dryness |  |
| Desquamation |  |
| Roughness |  |
| Others |  |
| Please define: | | | | | |

On D0, the subjects are also asked about their usual functional habits:

| | NONE | VERY MILD | MILD | MODERATE | SEVERE |
|-------------------------|--------------------------|--------------------------|--------------------------|--------------------------|--------------------------|
| Tightness |  |
| Stinging |  |
| Itching |  |
| Warm, burning sensation |  |
| Others |  |
| Please define: | | | | | |

At the end of the study, the cutaneous acceptability of the product is assessed by taking into account the relevant elements reported by the subject (functional and physical signs) as well as those noted during the examination (clinical signs).

The confrontation of these signs is used to conclude the final cutaneous acceptability of the studied product.

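### Section 2.4 draws one acceptability conclusion with no split by group or side, although 8 of 12 patients also receive a lamp titrated to erythema, itself a scored acceptability sign

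*Combined protocol and SAP*

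**What the plan says.** **Objectives.** The synopsis makes repigmentation primary: "Evaluate the percentage of repigmentation observed one month after the end of three months of treatment". Among the secondary objectives it lists "the ability of the product to maintain the human body in good condition (cutaneous acceptability) by clinical examination by the dermatologist". Section 1 names only this second property as the aim and attaches a use condition to it: "Its aim is to further confirm, under normal and reasonably foreseeable use conditions, the capacity of products to maintain human body in good condition". No section defines that use condition.

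**Who receives the lamp.** The synopsis plans "Number of subjects minimum 12 distributed into groups of 4". Section 1.2.2 gives Groups A and B the "excimer lamp on target lesions on the two sides", so the product side and the placebo side are both irradiated. Group C has no lamp. Section 1.3 confirms this: "Patients of both groups A and B come to the hospital where the lesions will be exposed with a Quantel 308 excimer lamp", twice a week.

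**How the lamp is dosed.** Section 2.3 increases the dose every two sessions until a frank erythema is reached that lasts under 48 hours and does not blister.

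**How acceptability is judged.** Section 2.4 grades erythema first, then edema, dryness, desquamation and roughness. It also asks about sensations such as stinging and burning. It closes with one statement: "The confrontation of these signs is used to conclude the final cutaneous acceptability of the studied product". The acceptability row of Section 1.4 expects no worsening from baseline and names no subgroup or side. Section 1.4.2 limits all analysis to description.

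**The concern.** In Groups A and B the co-treatment is deliberately raised until it produces a sign that the acceptability assessment counts. A single conclusion over both use conditions can then mislead in two directions. Lamp erythema may be charged to the product, which then seems to fail the expectation in Section 1.4 although it is well tolerated alone. Or the assessor may discount erythema as expected from the lamp and call the product acceptable. That verdict would then be quoted for use without the lamp, although two thirds of the patients did not use it that way.

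The design has the means to separate the two effects, namely a lamp-free group and a placebo side in every patient. The acceptability sections use neither.

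**Working it through.** **1. Group counts.** Inputs: the randomization list in Appendix 5.1.
- Group A: subjects 1, 4, 5, 8 (4 patients, lamp)
- Group B: subjects 2, 6, 7, 12 (4 patients, lamp)
- Group C: subjects 3, 9, 10, 11 (4 patients, no lamp)

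The total is 4 + 4 + 4 = 12, which reproduces the synopsis figure. With lamp: 8/12 = 66.7%. Without lamp: 4/12 = 33.3%.

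**2. Is there a split?** Sections 1.4 and 2.4, set side by side:
- By group or lamp: none in either section.
- By side: Section 2.4 examines the subject's body, and its grid has no side column in the text. A figure at that place could not be seen, so this should be checked against the form itself. By contrast, Section 2.5 asks for satisfaction on the left and right sides separately.

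**3. What mixing does.** Let q be the share of lamp patients with worsening and r the share in Group C. The pooled share is (8q + 4r)/12. The documents give no rates, so q and r are assumptions:

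| q (A and B) | r (C) | Pooled |
|---|---|---|
| 50% | 0% | 4/12 = 33% |
| 80% | 0% | 6.4/12 = 53% |
| 100% | 0% | 8/12 = 67% |

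In each row the product used without the lamp causes no worsening, yet the pooled figure contradicts the result expected in Section 1.4.

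**4. What Group C alone can show.** With zero reactions in n patients, the exact upper 95% limit is 1 − 0.05^(1/n) one-sided and 1 − 0.025^(1/n) two-sided. For n = 4:
- one-sided: 1 − 0.05^(1/4) = 52.7%
- two-sided: 1 − 0.025^(1/4) = 60.2%

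The chance that Group C shows at least one reaction is 1 − (1 − p)^4. At an assumed true rate p of 10% this is 34.4%; at 20% it is 59.0%. A clean result in Group C is therefore weak evidence of good tolerance.

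**The case against.** **Pooling is not written down.** Section 2.4 names no pooled population or rate. Section 1.4 promises individual values, and Appendix 5.1 gives each subject's group, so a reader could separate Group C. This is correct: pooling is inferred from the single conclusion and the absence of any split. But individual tables do not change what the stated conclusion covers.

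**Only Group C answers the stated aim.** A reader might infer this from the use-condition wording in Section 1. The documents do not support it. The phrase also covers reasonably foreseeable use, is nowhere defined, and introduces the very sections that contain the lamp groups. Similar wording recurs in the definition of an undesirable effect in Section 6.1.2, so it may be standard text. The UV restrictions in Sections 1.1.1 and 1.1.2 do not settle the matter: they concern exposure that a patient plans and excessive exposure, and neither clearly refers to the study lamp.

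**The placebo side already controls for the lamp.** Both sides are irradiated in Groups A and B, so a within-patient comparison could isolate what the product adds. This is a strong point, and it is why recording by side belongs in the fix. It does not answer the concern as the plan stands, because no comparison by side is specified for acceptability. Even with one, the result in A and B describes tolerance under the lamp.

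**A pooled zero-event contrast.** A reader might set zero of 12 (upper limits 22.1% and 26.5%) against zero of 4 (52.7% and 60.2%) and say that pooling more than halves the limit. The arithmetic is right, but zero signs in all 12 is unlikely when the lamp is titrated to erythema. The plan also claims no reaction rate. Only the Group C limit is relied on here.

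**Transience.** Erythema that lasts under 48 hours may have faded by a visit, so the contamination could be smaller than the illustrations. That is possible, but Section 2.4 also takes in signs that the subject reports.

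**Conclusion.** The concern holds in a limited form. Read as written, the acceptability conclusion mixes an intended effect of the lamp, present in 8 of 12 patients, with tolerance of the product. What can be said about the product without the lamp rests on 4 patients, where even a clean result leaves an exact upper 95% limit of 53% (one-sided) or 60% (two-sided). Group C uses the product twice daily only, so once-daily use without the lamp is not studied at all.

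This rests on three assumptions: the single conclusion is drawn over all groups, the acceptability form has no entry by side, and the 12 listed patients are all assessed. How far lamp reactions would distort the conclusion cannot be fixed from the documents, and the pooled rates shown are illustrations.

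The point concerns a secondary, descriptive outcome in a proof-of-concept study and leaves the repigmentation endpoint untouched. The mismatch between the Section 1 aim and the synopsis objectives is editorial and would not merit a comment alone. The reporting split does, because it changes what may be concluded.

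**What to change.** 1. In Section 2.4, record each clinical and reported sign separately for the right and left sides, as Section 2.5 already does for satisfaction.
2. In Sections 1.4 and 2.4, report acceptability separately for Group C (product without lamp) and Groups A and B (product with lamp). For each, give the number of patients with worsening on the product side, the number with worsening on the placebo side, and the number whose product side is worse than the placebo side. Add exact 95% confidence intervals and label them as description only.
3. Limit any statement about the product without the lamp to Group C, and give its n.
4. In Section 1, state which groups the use-condition wording covers, and reconcile the aim with the primary and secondary objectives of the synopsis.

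No patients, visits or change of design are needed. The cost is a slightly longer form and table. It also becomes visible that the statement on the product without the lamp rests on 4 patients.

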1.1. POPULATION

1.1.1. Selection

| INCLUSION CRITERIA | |
|---|--|
| Specific | |
| | |
| • Sex: female and male; | |
| • Age: 18 years old and above; | |
| • Patients with stable non-segmental vitiligo lesions (defined by no new lesions or lesions existing for at least 3 months, absence of hypochromic margins in Wood's light and absence of confetti depigmentation); | |
| • Patients with 2 to 6 symmetrical lesions (1 to 3 on each side). These lesions (macules) will be treated for a minimum surface of 2 cm ² and a maximum surface of 100 cm ² . | |
| General | |
| • Healthy subject; | |
| • Subject having given his/her free informed, written consent; | |
| • Subject willing to adhere to the protocol and study procedures. | |

NON-INCLUSION CRITERIA

- pregnant or nursing woman or woman planning to get pregnant during the study;
- Patient with segmental or mixed vitiligo;
- Patient with vitiligo on the external genitalia;
- Patient with vitiligo on hands and feet only;
- Patient with a history of skin cancer or pre-cancerous skin lesions;
- Patient taking topical or systemic vitiligo treatments within the previous month of the study;
- Patient taking concomitant local or general corticosteroid therapy or immunomodulatory treatment;
- Patient with a history of photodermatoses or taking photosensitizing medications;
- Patient planning to expose himself (artificial sun or UV) during the study on the zones to be treated and / or having been exposed during the previous month to the study and having an obvious acquired pigmentation (tanning);
- Patient who had been treated with phototherapy within 4 weeks before randomization;
- Patient with lithium allergy.

1.1.2. Study requirements and constraints

| DURING THE STUDY, THE SUBJECTS | | |
|---|---|---|
| HAVE TO | MUST NOT | ARE ALLOWED TO USE* (except on visiting days) |
| 
 • respect dates and hours of hospital visits; • follow the conditions of use of the investigational product at home; • complete the daily-log and bring it back with the investigational product at the end of the study; • avoid excessive UV exposure (including artificial UV). | 
 • apply any product to test areas the days of the visits* to the hospital; • apply any other similar product to test areas; • modify their usual make-up, hygiene or care products and/or use new products; • allow the use of the investigational product by another person than himself/herself. | 
 • usual cleansing products. |

1.1.3. Compliance assessment

The compliance is controlled by checking the daily log and by weighing the products before distribution (D0) and after use (M3).

+ See Appendix 5.2.

1.1.4. Protocol deviations

A protocol deviation can be defined as any non-adherence to the final protocol, including:

- wrong inclusion (inclusion criteria or non-inclusion criteria not fulfilled);
- start of a prohibited concomitant treatment;
- non-adherence of the subjects to the study schedule (missed or postponed visit);
- missing data for one or several evaluation criteria;
- low compliance of the subject to the study product(s) application;
- premature study end or untraceable subject;
- no respect of the constraints envisaged by the protocol.

Deviations to the protocol should be classified as:

- **minor** if they don't impact the rights, safety or well-being of the subjects. They do not increase the risk for the subject and/or do not have a significant effect on the integrity of the data collected,
- **major (or protocol violations)** if they affect the rights, safety or well-being of participants. They increase the risk for the subject and/or have a significant effect on the integrity of the study data.

In case of minor protocol deviation, the technician or the investigator repeats the instructions and reminds the subject to follow protocol requirements / study procedures. In case of persistent or major protocol violations, the subject is declared non-compliant and withdrawn from the study because of non-compliance.

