1.4. DATA ANALYSIS

The following data are analyzed:

| | Parameter(s) | Unit(s) | Variation(s) DX/D0 Kinetics | Statistical analysis (tick if yes) | Expected result(s) |
|--------------------------------|---|-----------------|-----------------------------------|--|--------------------|
| Cutaneous acceptability | Clinical signs observed Functional and physical signs reported | / | D28/D0 | / | No worsening |
| Efficacy | Lesions surface | cm ² | M4/D0 M3/D0 M2/D0 M1/D0 | / | Decrease |
| Subjective evaluation | Analog visual scale from 0 to 10 | Score | / | / | / |

Individual data are presented in raw value tables. These tables also show the descriptive statistics: means, medians, minima, maxima, standard errors of the means (SEM) and confidence intervals of 95% (95% CI).

Variation tables present raw variations, percentage variations and descriptive statistics.

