5. APPENDICES – STUDY DOCUMENTS

5.1. RANDOMIZATION LIST (GROUPS ATTRIBUTION)

RANDOMIZATION LIST
STUDY 18E1721
17/09/2019

| ID | Groupe | Côté Droit | Côté Gauche |
|----|--------|------------|-------------|
| 1 | A | Produit A | Produit B |
| 2 | B | Produit B | Produit A |
| 3 | C | Produit A | Produit B |
| 4 | A | Produit B | Produit A |
| 5 | A | Produit B | Produit A |
| 6 | B | Produit A | Produit B |
| 7 | B | Produit B | Produit A |
| 8 | A | Produit A | Produit B |
| 9 | C | Produit B | Produit A |
| 10 | C | Produit A | Produit B |
| 11 | C | Produit B | Produit A |
| 12 | B | Produit A | Produit B |

Groupe A: 1 application/ jour (le soir) + lampe

Groupe B: 2 applications/ jour (matin et soir) + lampe

Groupe C: 2 applications/ jour (matin et soir)

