6.2. PREMATURE TERMINATION OF SUBJECT PARTICIPATION

In compliance with the Helsinki Declaration (1964) and its successive updates, subjects have the right to exit from the study at any time and for any motive.

The investigator can also interrupt the subject participation in the study prematurely in the case of a disease occurrence, a pregnancy or the occurrence of an adverse reaction.

The Sponsor can demand that any subject be excluded from the study for major infringements to the protocol, for administrative reasons or any other motive however this would need to be clearly documented with a rationale as to why.

Nevertheless, premature removal of a high percentage of subjects from the study can make it difficult or impossible to interpret. Consequently, any premature exit without valid motives should be avoided as much as possible and is carefully documented in the case report form, the final report and, if necessary, in the Adverse Event form.

Every premature exit must be classified under one of the following headings:

- presence of a non-inclusion criteria;
- Undesirable Effect / Adverse Event occurrence;
- Serious Adverse Event / Serious Adverse Effect occurrence;
- withdrawal of consent;
- lost to follow-up;
- appearance of non-inclusion criteria;
- non-adherence to the protocol;
- other reason.

No replacement is foreseen as 10% additional subjects are planned to be included in the study.

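### Subjects withdrawn from the study for non-compliance before M4 have no primary outcome, because the plan does not provide for the M4 tracing after withdrawal

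*Combined protocol and SAP*

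**What the plan says.** Section 1.1.4 lists what counts as a protocol deviation. The list includes "low compliance of the subject to the study product(s) application", missed or postponed visits and missing evaluation data. For a minor deviation the instructions are repeated to the subject. The next step is: "In case of persistent or major protocol violations, the subject is declared non-compliant and withdrawn from the study because of non-compliance". The withdrawal is from the study, not only from the product.

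The primary objective, in the summary table at the front, is: "Evaluate the percentage of repigmentation observed one month after the end of three months of treatment". That is the M4 visit. The same table gives the size: "Number of subjects minimum 12 distributed into groups of 4".

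Section 6.2 lists non-adherence to the protocol as a heading for premature exit and says: "No replacement is foreseen as 10% additional subjects are planned to be included in the study". It also warns that "premature removal of a high percentage of subjects from the study can make it difficult or impossible to interpret".

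Sections 1.4 and 1.4.2 plan descriptive statistics only, among them "confidence intervals of 95% (95% CI"). They define no analysis set and no rule for missing data. Nothing in 1.1.4, 1.3, 1.4 or 6.2 says whether a withdrawn subject is still traced at M4.

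**The concern.** Non-compliance arises after randomisation. If it ends follow-up, the patients who contribute to the M4 result are selected by behaviour during the trial. That behaviour may be linked to tolerance or to lack of visible response. The result then describes those who kept to the regimen rather than those who were randomised.

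The groups are also very small. One patient is a quarter of a group (1/4 = 25%). Since no test is planned, the means and intervals are the whole efficacy result, and losing one patient of four affects exactly that output. The loss is also avoidable, because the M4 visit is already scheduled and the tracing does not depend on whether the patient used the product as instructed.

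**Working it through.** The plan gives no power, precision, SD or effect size, so there is no stated figure to reproduce beyond the count. The checks below are on the list and on interval width.

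**1. The randomisation list (5.1).** Group A is IDs 1, 4, 5, 8; group B is 2, 6, 7, 12; group C is 3, 9, 10, 11. That is 4 + 4 + 4 = 12. Within each group, Produit A is on the right side for two patients and on the left for two. One loss leaves 2:1.

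**2. The 10% allowance (6.2).** 12 × 1.10 = 13.2 and 12 / 0.90 = 13.3, so either way 14 subjects. The list ends at ID 12 ("12 | B | Produit A | Produit B"), so it contains no spare numbers.

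**3. Interval width, main reading.** Assumptions: one value per patient (the product-minus-placebo difference of 1.4.1), one interval per group, a t interval, and the same SD before and after the loss. Half-width = t(0.975, n−1) × SD / √n.

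- n = 4: 3.182 / 2 = 1.591 SD
- n = 3: 4.303 / 1.732 = 2.484 SD; ratio 2.484 / 1.591 = 1.561, or +56%
- n = 2: 8.985 SD; ratio 5.65

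**4. Other readings.** The plan states neither the formula, nor the unit of analysis, nor the grouping.

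| Reading | Change in half-width after losing one patient |
|---|---|
| t interval, 4 to 3, allowing for the SD being estimated (expected width) | +50% |
| t interval, group of 5 falling to 4 | +28% |
| t interval on lesions, 8 to 6 (two per side) | +26% |
| t interval on lesions, 12 to 9 (three per side) | +21% |
| Normal quantile, 4 to 3: √(4/3) = 1.155 | +15% |
| t interval, all groups pooled, 12 to 11: 0.672 / 0.635 | +6% |

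These are averages or fixed-SD values. In a simulation with normal data, the observed interval became narrower in about 15% of cases, because the lost patient may be the outlying one.

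**5. Chance of a loss.** The documents give no rate of removal for non-compliance. Taking a removal probability p per patient as an assumption, with patients independent, the chance of at least one loss is 1 − (1−p)^4 in a given group and 1 − (1−p)^12 overall. For p = 5% this is 19% and 46%; for 10%, 34% and 72%; for 20%, 59% and 93%.

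**6. Timing.** The daily log comes back at M1, M2 and M3, so low use recorded there can lead to withdrawal before M4. Section 1.1.3 dates the second weighing at M3, whereas 1.3 puts weighing after use at the end of the study, after M4. Low use seen only by weight could therefore surface before or after the primary tracing.

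**The case against.** The strongest reply is that the comparison is within patients and double blind. Both sides of a patient leave together, so removal does not unbalance product against placebo. This stands. A reader might infer bias between product and placebo sides, and the documents do not support that. Nor do they show that one group would lose more patients than another. Groups A and B attend for the lamp twice a week and C does not, so a difference is possible, but it is undocumented and no between-group test is planned.

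Second, 1.1.4 does not say that collected data are deleted. A reader might infer that the M4 endpoint of every non-compliant patient is discarded. That goes too far: minor deviations first lead to repeated instructions, and a violation found after M4 costs no tracing. The loss arises only for withdrawals made before M4.

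Third, extra subjects are foreseen and 12 is a minimum. That could restore numbers, though the current list has no slots for them and extra subjects would not undo the selection. The 10% is an allowance for all premature exits. It should not be read as the rate at which this rule removes patients.

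Fourth, the rule also covers major violations that affect rights, safety or well-being. This is a sound reason not to replace it, but it does not argue against tracing the lesions of a withdrawn patient who still consents.

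Finally, the warning in 6.2 concerns removal of a high percentage of subjects, not any single exit. With four per group, though, one exit is already 25% of the group.

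**Conclusion.** The point holds for patients withdrawn before M4. As written, the plan leaves them without a primary outcome although both sides were randomised and traced at D0. The consequences are lost precision and a result restricted to compliers.

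The size is +56% in half-width (1.59 to 2.48 SD) for one loss in a group of 4, on the assumption of a patient-level t interval per group at an unchanged SD. It would be tempting to call this a property of the planned interval, but the plan does not specify one. Other readings run from +6% (pooled) to +50% (expected width). The figure would also apply to a patient lost for any reason, so it shows how fragile a group of four is and not how often this rule would act. How often that would be is unknown, and the probabilities above are assumptions only.

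For a descriptive proof of concept this is not fatal, but it should be corrected because the remedy is cheap.

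**What to change.** Leave the existing rules on stopping product and on safety unchanged, and limit the change to outcome collection and the analysis set.

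- **Section 1.1.4, add:** a subject withdrawn for non-compliance is still invited to the remaining planned assessments, including the M4 tracing, unless consent is withdrawn.
- **Sections 6.1.7 and 6.2, reconcile with this addition.** 6.1.7 has a subject drop out immediately on pregnancy. 6.2 lets the sponsor require exclusion for major infringements and lists non-adherence as an exit heading. The text should say how outcome collection relates to each. The 10% allowance should also be reconciled with the 12-line list.
- **Section 1.4, add:** all randomised patients with an M4 tracing are analysed in their group and sides as randomised; a compliers-only table is secondary. State the interval formula, the unit (patient or lesion) and the grouping.

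The cost is a few sentences and visits that are already scheduled. The change recovers nothing for patients who withdraw consent or cannot be traced. Estimates will include imperfect users, and with four per group a single major deviator can visibly shift a group mean. The secondary table would show that.
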